## 8.6 Overdose

- An overdose with associated AEs is recorded as the AE diagnosis/symptoms on the relevant AE modules in the eCRF and on the Overdose eCRF module.
- An overdose without associated symptoms is only reported on the Overdose eCRF module

If an overdose on a Sponsor study drug occurs in the course of the study, the Investigator or other site personnel inform appropriate Sponsor representatives immediately, but **no later than 24 hours** of when he or she becomes aware of it.

The designated Sponsor representative works with the Investigator to ensure that all relevant information is provided to the Sponsor's representative Patient Safety data entry site **within one or 5 calendar days** for overdoses associated with an SAE (see Section [8.5.9](#)) and **within 30 days** for all other overdoses.

## 8.7 Human Biological Samples

Instructions for the collection and handling of biological samples will be provided in the study specific laboratory manual. Samples should be stored in a secure storage space with adequate measures to protect confidentiality. For further details on Handling of Human Biological Samples see [Appendix D](#).

Samples will be stored for a maximum of 15 years from the date of the issue of the CSR in line with consent and local requirements, after which they will be destroyed/repatriated.

- PK samples will be disposed of after the bioanalytical report finalisation or 6 months after issuance of the draft bioanalytical report (whichever is earlier), unless consented for future analyses.
  - PK samples may be disposed of or anonymised by pooling. Additional analyses may be conducted on the anonymised, pooled PK samples to further evaluate and validate the analytical method. Any results from such analyses may be reported separately from the CSR.

- Remaining anti-drug antibody (ADA) sample aliquots will be retained at Fusion Pharmaceuticals or its designee for a maximum of 15 years following issue of the CSR. Additional use includes, but is not limited to, further characterisation of any ADAs, confirmation and/or requalification of the assay as well as additional assay development work. The results from future analysis will not be reported in the CSR.

### 8.7.1 Pharmacokinetics

- Blood samples will be collected for measurement of serum concentrations of [In]-FPI-2107 and [Ac]-FPI-2068 as specified in the SoAs (see Section 8.1).
- Samples may be collected at additional time points during the study if warranted and agreed upon between the Investigator, Medical Monitor, and the Sponsor, e.g., for safety reasons. The timing of sampling may be altered during the course of the study based on newly available data (e.g., to obtain data closer to the time of peak or trough matrix concentrations) to ensure appropriate monitoring.
- Serum samples will be used to analyse the PK of [In]-FPI-2107 and [Ac]-FPI-2068. Samples collected for analyses of [In]-FPI-2107 and [Ac]-FPI-2068 serum concentrations may also be used to evaluate safety or efficacy aspects related to concerns arising during or after the study.
- Samples will be collected, labelled, stored, and shipped as detailed in the laboratory manual.
- If feasible, a blood sample should be collected for PK analysis as soon as possible when a participant is suspected of having ILD/pneumonitis, if there are no other PK samples on the same day (see SoA [Table 26](#), [Table 27](#), and [Table 28](#), and Section 8.4.6.1). PK samples should be taken only while the patient remains on treatment (e.g., within 56 days of the last dose).

#### 8.7.1.1 Determination of Drug Concentration

Samples for determination of drug concentration by radioanalysis and by antibody determination using assays targeting total bsAb and conjugated bsAb assays will be assayed by bioanalytical test sites operated by or on behalf of Fusion Pharmaceuticals, using an appropriately validated bioanalytical method. Full details of the analytical methods used will be described in a separate bioanalytical report.

Incurred sample reproducibility analysis, if any, will be performed alongside the bioanalysis of the test samples. The results from the evaluation, if performed, will be reported in a separate bioanalytical report.

### 8.7.2 Immunogenicity Assessments

Blood samples for determination of ADA in serum will be assayed by bioanalytical test sites

operated by or on behalf of the Sponsor, using an appropriately validated bioanalytical method. Full details of the methods used will be described in a separate report. ADA samples may also be further tested for characterisation of the ADA response. Samples will be collected, labelled, stored, and shipped as detailed in the laboratory manual.

### **8.7.3 Pharmacodynamics**

For collection of biological samples for biomarker analysis, including ctDNA, see Section [8.8](#).

## **8.8 Human Biological Sample Biomarkers**

By consenting to participate in the study the participant consents to the mandatory research components of the study. Samples for biomarker research are required and will be collected from all participants in this study as specified in the SoAs (see Section [8.1](#)).

### **8.8.1 Collection of Mandatory Samples for Biomarker Analysis**

Samples will be tested to determine the systemic pharmacodynamic parameters and biomarkers of clinical response to FPI-2068 when administered as monotherapy or with other anticancer agents to evaluate their association with changes in peripheral biomarkers, including but not, limited to variations in the allelic frequency of ctDNA, soluble and cellular analytes, and changes in gene expression as deemed appropriate. These biomarker measurements will support understanding of the mechanism of action and may guide further identification of participants who are most likely to respond to FPI-2068.

The participant's consent to the use of donated biological samples is mandatory. Details regarding specimen collection, processing, and testing will be provided in the laboratory manual.

The following samples are mandatory and will be collected from all participants (unless otherwise noted) at timepoints specified in the SoAs (see Section [8.1](#)) for each study part:

- Whole blood for RNA and T-cell receptor sequencing (see Section [8.8.1.1](#))
- Plasma for ctDNA and circulating biomarkers (see Section [8.8.1.2](#))
- Serum for tumour marker analysis (see Section [8.8.1.3](#))
- Archival tumour samples for exploratory analysis (see Section [8.8.1.4](#)).

#### **8.8.1.1 Collection of Blood for RNA and T-cell receptor sequencing**

A peripheral blood sample will be collected to provide PBMCs for TCR sequencing. Baseline and on-treatment whole blood for PBMCs will be collected predose at the timepoints indicated in the SoAs (see Section [8.1](#)) for each study part. A peripheral blood sample will be collected in PAXgene tubes and stored frozen for RNA sample preparation. Baseline and on-treatment whole blood RNA will be collected predose at the timepoints indicated in the SoAs (see Section [8.1](#)) for each study part. Testing may include (but is not limited to):

- Evaluation of the immune cellular repertoire to monitor T-cell clone expansion and/or T-cell activation
- Analyses of transcript and/or RNA expression and stored for future analyses.
- Messenger RNA levels of selected inflammatory/immune and cytokine pathways that may include, but are not limited to, IFN- $\gamma$ , IFN- $\gamma$  inducible genes, and effector T-cell or dendritic cell gene signatures will be measured in relation to their association with clinical outcome.

#### **8.8.1.2 Collection of Plasma Samples for ctDNA**

A peripheral blood sample will be collected to provide plasma for ctDNA. Baseline and on-treatment plasma for ctDNA will be collected predose and at timepoints indicated in the SoAs (see Section 8.1) for each study part. The final sample will be taken at disease progression.

Testing may include (but is not limited to):

- Whether there is sufficient ctDNA in plasma for mutational testing.
- Correlation of baseline ctDNA levels and kinetics of ctDNA changes with clinical outcome measures.
- Correlation between tumour and plasma mutational status.
- Genetic alterations as potential mechanisms of sensitivity or resistance to FPI-2068 treatment.
- Future diagnostic development.

#### **8.8.1.3 Collection of Serum Samples for Tumour Marker Analysis**

A peripheral blood sample will be collected to provide serum for tumour marker analysis. Baseline and on-treatment serum for tumour marker analysis will be collected predose and at timepoints indicated in the SoAs (see Section 8.1) for each study part.

Testing may include (but is not limited to):

- Carbohydrate antigen-19-9 (CA-19-9).
- Carcinoembryonic antigen (CEA)

#### **8.8.1.4 Collection of Archival Tumour Samples**

Provision of a tumour tissue sample (block or unstained slides) at baseline is mandatory for all participants. Expression of EGFR and MET will be evaluated from the baseline tumour samples using validated central laboratory IHC assays. Where a participant has multiple archival tissue samples with sufficient tumour content available, tissue from the most recent biopsy is preferred. If archival tissue obtained within the last 12 months is not available, a

fresh biopsy will be required for IHC and biomarker analyses. Availability of tissue must be confirmed prior to administration of FPI-2053 or [In]-FPI-2107; however, the participant may receive study treatment prior to any analysis of the tissue.

Additional exploratory analyses will be performed on the archival tumour tissue samples, including but not limited to genomic and or protein analysis of tumour tissue to identify markers of response and resistance to study intervention. The tumour samples may also be used for future diagnostic test development and/or validation.

### **8.8.2 Collection of Optional Biomarker Samples**

The on-study provision of tumour tissue is encouraged only if clinically appropriate and not considered detrimental to participant care. The biopsied tumour must not be used as part of the RECIST v1.1 assessments. Participants will not be excluded from the study if these samples are not collected.

Refer to the Investigator laboratory manual for further details of on-study tumour tissue collection, shipping, and storage.

#### **8.8.2.1 Collection of On-study Tumour Samples**

##### Tumour Biopsy on Treatment

If a tumour sample can be safely obtained, every effort should be made to collect a core biopsy between Day 8 and Day 11 in Cycle 1 or Cycle 2 of the Treatment Period. Inability to obtain a biopsy will not be noted as a protocol deviation; however, a minimum of 6 paired biopsies must be obtained during the backfill cohort (Predose and Cycle 1 or Cycle 2 between Days 8 and 11).

##### Tumour Biopsy on Disease Progression

Where possible, a further on-study tumour biopsy sample from the progressing lesion should be taken at the time of documented RECIST v1.1 progression in participants that have provided the additional optional consent. Biopsies at progression may be particularly valuable when there is a marked phenotypic change in a particular lesion, and Investigators are encouraged to contact Fusion in these cases.

#### **8.8.2.2 Collection of Blood for RNA**

An optional whole blood sample may be collected in a PaxGene DNA tube to aid in somatic variant calling of tumour tissue samples. Where possible, this sample should be collected at the same time as the collection of any optional tumour biopsy sample.

#### **8.8.2.3 Collection of Blood for ILD Investigational Biomarker Analysis**

If feasible, additional blood samples for exploratory biomarker analysis should be taken as soon as possible when a participant is suspected of having ILD/pneumonitis (see SoA, [Table 26](#), [Table 27](#), and [Table 28](#) and Section 8.4.6.1).

## **8.9        Optional Genomics Initiative Sample**

Optional Genomics Initiative research is not applicable in this study.

## **8.10      Medical Resource Utilisation and Health Economics**

Medical Resource Utilisation and Health Economics parameters are not evaluated in this study.

# **9            STATISTICAL CONSIDERATIONS**

The statistical analyses will be performed by Fusion Pharmaceuticals or its delegated representatives (Contract Research Organisation [CRO]) under the direction of Fusion Pharmaceuticals. Statistical Methods will be detailed in the Statistical Analysis Plan (SAP).

## **9.1        Statistical Hypotheses**

Not applicable.

## **9.2        Sample Size Determination**

The primary objective of this study is to investigate the safety, tolerability, and dosimetry, and thereby estimate the MTD and determine the RP2D, of [Ac]-FPI-2068. Hence, the number of participants has been based on the desire to obtain adequate tolerability, safety, and PK data while exposing as few participants as possible to the investigational product and study procedures.

Approximately 150 participants will be screened to achieve approximately 125 safety-evaluable participants and approximately 110 efficacy-evaluable participants across all parts of the study. This assumes an approximate 20% and 10% general and imaging screen fail rate, respectively.

The total number of participants depends upon the number of dose escalations/de-escalations necessary. Approximately three participants in up to 3 dose cohorts are required in Part A. At least three, and up to nine, evaluable participants are required for each dose cohort (unless unacceptable toxicity is seen before three evaluable participants) in Part B. If a preliminary signal of activity is observed, backfill of one or more dose level at any dose level at or below the projected MTD (approximately 20 evaluable participants per dose level) is permissible per the predefined efficacy criteria outlined in Section 4.1.1. The actual number of dose levels and participants enrolled during dose escalation will depend upon the number of DLTs in each cohort, the dosimetry at each dose level, and the overall safety profile observed, including the emergence of late-onset toxicities, as the study progresses.

## **9.3        Populations for Analyses**

For purposes of analysis, the study populations are defined as provided in Section 5. The analysis sets are described in [Table 30](#).

**Table 30 Analysis Sets**

Analysis set	Description
Enrolled	All participants who signed the informed consent form
DLT evaluable	A participant who receives [  Ac]-FPI-2068 and completes the DLT observation period without a DLT or a participant who experiences a DLT
Safety	All enrolled participants that receive any amount of [  In]-FPI-2107 with or without [  Ac]-FPI-2068
Efficacy evaluable	All participants who received at least one dose of [  Ac]-FPI-2068 and either have at least one postbaseline efficacy assessment or discontinued from the study prematurely due to toxicity, disease progression, or death
PK	All participants who received at least one dose of [  In]-FPI-2107 or [  Ac]-FPI-2068 and have at least one reportable PK concentration

DLT, dose limiting toxicity; PK, pharmacokinetics.

## 9.4 Statistical Analyses

The SAP will include a more technical and detailed description of the statistical analyses described in this section. This section is a summary of the planned statistical analyses of the most important endpoints including primary and key secondary endpoints.

### 9.4.1 General Considerations

This study will employ an mTPI-2 design. The mTPI-2 design employs a simple beta-binomial Bayesian model. The posterior density of the toxicity probability is divided into multiple intervals with equal length. These intervals are categorised as underdosing, proper dosing, and overdosing in terms of toxicity. The underdosing interval corresponds to a dose escalation, overdosing corresponds to a dose de-escalation, and proper dosing corresponds to staying at the current dose. The design for the dose escalation phase of the study uses a target DLT rate of 30% and an equivalence interval (25%, 35%) for dose escalation/de-escalation decisions as well as MTD determination. A dose level is considered unsafe, with no additional participants enrolled at that dose level, if it has an estimated 95% or more probability of exceeding the target DLT rate of 30% (i.e.,  $P[DLT > 30\% \text{ data}] \geq 95\%$ ).

All collected data will be reported using summary tables and figures, as appropriate. Data summaries will be presented separately by cohort and/or dose level, as applicable. Tabulations will be produced for appropriate disposition, demographic, baseline, PK, ADA, efficacy, and safety parameters.

Categorical variables will be summarised by frequency distributions (number and percentages of participants) and continuous variables will be summarised by descriptive statistics (mean, standard deviation, median, minimum, and maximum). For PK concentration and PK parameters, geometric mean and coefficient of variation will be reported. For time-to-event variables, percentages of participants experiencing that event will be presented and time-to-event endpoints will be estimated using the Kaplan-Meier method. Graphical displays will be

presented, as appropriate. All data will be provided in by-participant listings.

#### 9.4.2 Efficacy Analyses

The secondary efficacy endpoints of ORR, time to response (TTR), duration of response (DoR), PFS, disease control rate (DCR), OS, and percentage change in total ctDNA (variant allelic frequency) from baseline will be summarised on the Efficacy Evaluable Analysis Set (i.e., all participants who received at least one dose of [Ac]-FPI-2068 and either have at least one postbaseline efficacy assessment or discontinued from the study prematurely due to toxicity, disease progression, or death).

ORR is defined as the proportion of participants with a best response of complete response (CR) or PR per RECIST Version 1.1 that occurs prior to the initiation of subsequent anti-cancer treatment and prior to progression, with the denominator defined as the number of participants in the Efficacy Evaluable Analysis Set. ORR will be estimated, and 80% CI based on the exact binomial distribution will be presented by cohort.

The best overall response of CR or PR must be confirmed, which means a response of CR/PR is recorded at a visit and confirmed by repeat imaging not less than 28 days (4 weeks) after the visit when the response was first observed, with no evidence of progression between the initial and confirmation visit.

Analyses of other efficacy endpoints will include:

- TTR, defined as the duration of time from first treatment administration (i.e., [Ac]-FPI-2068) to first date of observed response (CR or PR). Participants that do not achieve response will be censored at last evaluable disease assessment.
- DoR, defined as the duration of time from first date of observed response (CR or PR) to first date of disease progression. Participants that do not experience disease progression will be censored at last evaluable disease assessment. Participants that do not achieve a response will not be included.
- PFS, defined as the duration of time from first treatment administration to first date of disease progression or death. Participants alive at the time of analysis that do not experience disease progression will be censored at last evaluable disease assessment.
- DCR, defined as the proportion of participants who achieve a PR, CR, or stable disease for at least 8 weeks. This parameter will be summarised using the same methods as described above for ORR.
- OS, defined as the duration of time from first treatment administration to date of death. Participants alive at the time of analysis will be censored at date of last contact.

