### 7.3 Lost to Follow-up

A participant will be considered lost to follow-up if he or she repeatedly fails to return for scheduled visits, as defined in Section 8, and is unable to be contacted by the study site.

The following actions must be taken if a participant fails to return to the clinic for a required study visit:

- The site must attempt to contact the participant and reschedule the missed visit as soon as possible and counsel the participant on the importance of maintaining the assigned visit schedule and ascertain whether the participant wishes to and/or should continue in the study.
- Before a participant is deemed lost to follow-up, the Investigator or designee must make every effort to regain contact with the participant (where possible, 3 telephone calls and, if necessary, a certified letter to the participant's last known mailing address or local equivalent methods). These contact attempts should be documented in the participant's medical record.
- Should the participant continue to be unreachable, he/she will be considered to have withdrawn from the study.

- Site personnel, or an independent third party, will attempt to collect the vital status of the participant within legal and ethical boundaries for all participants enrolled, including those who did not get investigational product. Public sources may be searched for vital status information. If vital status is determined as deceased, this will be documented and the participant will not be considered lost to follow-up. Sponsor personnel will not be involved in any attempts to collect vital status information.

Discontinuation of specific sites or of the study as a whole are handled as part of [Appendix A](#).

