### 8.2.2 Overall Survival

Assessments for survival will be conducted every 3 months for the first 2 years then every 6 months following treatment discontinuation. Survival information may be obtained via telephone contact with the participant, participant's family, by contact with the participant's current physician, or local death registries. Additional assessments, including subsequent anticancer therapy, are to be recorded.

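### OS and PFS are summarised on the Efficacy Evaluable set, whose membership depends on events after treatment, so some treated participants whose survival is followed or sought are left out

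*Protocol*

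**What the plan says.** Section 9.4.2 lists ORR, TTR, DoR, PFS, DCR, OS and ctDNA change and states that they "will be summarised on the Efficacy Evaluable Analysis Set". It defines that set in the same terms as Table 30: beyond one therapeutic dose, a participant must "either have at least one postbaseline efficacy assessment or discontinued from the study prematurely due to toxicity, disease progression, or death".

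The endpoint definitions in Section 9.4.2 do not depend on having been scanned:

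- "OS, defined as the duration of time from first treatment administration to date of death"; for censoring, "Participants alive at the time of analysis will be censored at date of last contact".
- "PFS, defined as the duration of time from first treatment administration to first date of disease progression or death"; those alive without progression are censored at the last evaluable disease assessment.

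Survival data are collected separately from imaging. Section 8.2.2: "Assessments for survival will be conducted every 3 months for the first 2 years then every 6 months following treatment discontinuation". For participants who cannot be reached, Section 7.3 has site staff or a third party try to establish vital status "for all participants enrolled, including those who did not get investigational product". Section 7.1 provides a modified follow-up (telephone, a relative, the treating physician or records) for participants who decline in-person visits, and says that they have not left the study.

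The protocol names no other set for OS or PFS. Table 30 has no set of all participants treated with [225Ac]-FPI-2068. Its Safety set cannot stand in for one, because it includes participants who received only [111In]-FPI-2107.

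**The concern.** A time-to-event summary that starts at first dose should include everyone who received that dose. Here, inclusion also depends on something observed later: being assessed, or the reason for leaving. That is selection on post-treatment events, and OS does not need it, since a date of death or last contact is enough.

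OS and PFS form part of the primary data analysis and the study report at the data cut-off (Section 4.4), and efficacy is one of the inputs to the RP2D (Section 4.1). Part B dose cohorts hold three to nine evaluable participants and a backfill cohort about 20, so one or two people can move an estimate.

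**Working it through.** **1. The plan's own number.** Section 9.2 gives about 150 screened, with general and imaging screen-failure rates of 20% and 10%, and about 110 efficacy-evaluable participants.

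150 × (1 − 0.20) × (1 − 0.10) = 108, which agrees with the stated 110.

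Screen failure alone accounts for the figure. The plan allows for no loss between treated and efficacy-evaluable, and gives no expected count for the exclusion at issue. An all-treated set would have essentially the planned size.

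**2. Who is in and who is out.** Take a participant dosed with [225Ac]-FPI-2068 who has no postbaseline efficacy assessment, read as a tumour assessment. The first is due at about Week 8 (Section 8.2.1).

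| What happens next | In the set? | Survival information |
|---|---|---|
| Leaves the study for toxicity, progression or death | Yes | Yes |
| Withdraws for another reason (Section 7.2) | No | Up to withdrawal; afterwards only where permitted |
| Lost to follow-up (Section 7.3) | No | Vital status sought |
| Stops treatment, stays in the study on modified follow-up (Section 7.1) | No, while alive | Followed (Section 8.2.2) |

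The last row holds even if treatment stopped for toxicity: the rule turns on leaving the study, which Section 7.1 distinguishes from stopping treatment.

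**3. Size for OS if these participants are simply dropped.** The protocol gives neither a drop rate nor a survival rate, so the values here are assumptions: 20 treated, d dropped, landmark survival 50% in those kept and S between 20% and 80% in those dropped.

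All-treated survival = [(20 − d) × 0.50 + d × S] / 20. The Efficacy Evaluable estimate is 50.0% throughout.

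| d | S = 20% | S = 80% |
|---|---|---|
| 1 | (9.5 + 0.2)/20 = 48.5% | (9.5 + 0.8)/20 = 51.5% |
| 2 | (9.0 + 0.4)/20 = 47.0% | (9.0 + 1.6)/20 = 53.0% |
| 3 | (8.5 + 0.6)/20 = 45.5% | (8.5 + 2.4)/20 = 54.5% |

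The shift is 0 to 4.5 points. The set overstates survival if the dropped do worse and understates it if they do better.

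**4. Size for OS if death brings a participant back in.** Read strictly, an unscanned participant on modified follow-up enters on death, because the study then ends for that reason, but stays out while alive. Take 2 such participants of 20, with 50% survival in both groups. Of the 18 others, 9 are alive and 9 dead; of the 2, the one who died enters and the one alive does not.

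Efficacy Evaluable: 9 / (9 + 9 + 1) = 9/19 = 47.4%. All treated: (9 + 1)/20 = 50.0%.

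Here membership depends on the outcome itself, and OS is biased downwards.

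**5. PFS.** A living participant with no postbaseline scan would be censored at or near time zero and contribute almost nothing. Only deaths after an excluded participant left can be lost, so the effect is smaller than for OS.

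**The case against.** The case against has four parts, and most of it limits the point rather than removing it.

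- **Stopping treatment early does not by itself exclude anyone.** A reader might infer that any participant who stops before Week 8 drops out of the analysis. The protocol does not support this. Under Section 7.1 the participant stays in the study, Table 25 schedules a CT or MRI at End of Treatment, and imaging continues in those who stopped for reasons other than progression. Exclusion requires withdrawal, loss or modified follow-up with no assessment at all. Section 7.2 expects withdrawal to be uncommon and allows an End of Treatment visit even then.
- **The rule says efficacy assessment, not scan.** The term is undefined. ctDNA change is listed among the efficacy endpoints and is sampled at Cycle 1 Day 15, and Section 8.2 on efficacy assessments includes overall survival. On that broad reading almost every treated participant qualifies. The point rests on the usual reading, tumour assessment; an OS population should not turn on which reading is taken.
- **Survival is sought, not known.** Section 7.3 provides for an attempt within legal and ethical limits. Under Section 7.2 a participant may withdraw consent to future disclosure, in which case only earlier data remain.
- **The consequence is modest.** OS and PFS are secondary and descriptive, no hypothesis is tested (Section 9.1), and by-participant listings will show all data.

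Two stronger readings also fail. One is that the set makes results look better. The set keeps those who leave for toxicity, progression or death, the main poor-outcome reasons, and the strict wording can bias OS downwards, so no direction is established. The other is that the ORR denominator is wrong too. An evaluable denominator for response is conventional, and a second ORR line on all treated would be a supplementary preference.

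**Conclusion.** The point holds in a limited form. The protocol itself assigns OS and PFS to a set defined by post-treatment events and offers no all-treated alternative, although neither endpoint needs that selection and survival is followed or sought. It does not show how many participants would be affected. The number is probably small, and the bias could go either way: up to about 4.5 points on a 50% landmark in a cohort of 20 with 1 to 3 left out, on assumed drop and survival rates. It concerns OS mainly and PFS less. The conclusion assumes that an efficacy assessment means a tumour assessment. This is a cheap improvement, not an error that threatens the trial's primary safety and dosimetry objectives.

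**What to change.** - In Table 30, add a set of all participants who received at least one dose of [225Ac]-FPI-2068.
- In Section 9.4.2, summarise OS and PFS on that set.
- State that for PFS a participant who is alive with no postbaseline tumour assessment is censored at first dose. The present rule, censoring at the last evaluable assessment, would point to a baseline scan taken before the PFS clock starts.
- Keep the Efficacy Evaluable set for ORR and DCR.

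The cost is a wording change. The data are already to be collected, the planned number hardly changes (108 by the plan's own rates against the stated 110), and the OS and PFS estimates may differ slightly from those on the current set.

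### Duration of response censors deaths and time to response censors participants who can no longer respond, so both Kaplan-Meier summaries err in the drug's favour

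*Protocol*

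**What the plan says.** The rules are in Protocol Section 9.4.2 (Efficacy Analyses), and the estimator is in Section 9.4.1 (General Considerations).

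- **DoR event.** "DoR, defined as the duration of time from first date of observed response (CR or PR) to first date of disease progression". Death is not an event.
- **DoR censoring.** "Participants that do not experience disease progression will be censored at last evaluable disease assessment". The sentence has no condition that the participant be alive.
- **TTR censoring.** "Participants that do not achieve response will be censored at last evaluable disease assessment".
- **Analysis set for both.** The Efficacy Evaluable set, which includes treated participants who "discontinued from the study prematurely due to toxicity, disease progression, or death".
- **Estimator.** "time-to-event endpoints will be estimated using the Kaplan-Meier method".
- **PFS, in the same list.** "PFS, defined as the duration of time from first treatment administration to first date of disease progression or death", with this censoring rule: "Participants alive at the time of analysis that do not experience disease progression will be censored at last evaluable disease assessment".

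The ORR definition in Section 9.4.2 counts a response only if it comes before progression and before any new anti-cancer treatment.

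**The concern.** **DoR.** A response can end in progression or in death. The planned definition recognises only the first. A responder who dies between scans is removed from the risk set as though the response might have continued, and the Kaplan-Meier curve is lifted. The same death is an event for PFS and a censoring for DoR, and the protocol does not explain the difference.

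**TTR.** Kaplan-Meier assumes that a censored participant has the same future chance of the event as those still under observation. A participant who has progressed or died has none, because a later response would not count. Censoring these people spreads their probability over those who remain, so one minus the Kaplan-Meier estimate overstates the proportion who respond.

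**What is at stake.** Both are named secondary efficacy endpoints. Section 4.1 says the RP2D will draw on all available efficacy information as well as safety, PK and dosimetry. The protocol itself expects early losses: the life-expectancy criterion is only 3 months (Section 5.1), and Section 6.7.6 gives rapid progression or death as examples of why a participant may not complete the 56-day DLT period.

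**Working it through.** The protocol gives no figure for DoR or TTR, so there is nothing to reproduce. The documents supply the rules above, a scan interval of about 8 weeks (Section 8.2.1) and a backfill size of about 20 evaluable participants per dose level (Section 4.1.1). All rates below are assumptions.

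**1. DoR**

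Take exponential times, and let *d* be the share of response-ending events that are deaths without documented progression. If deaths are censored, only the fraction 1 − *d* of the hazard is counted, so

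median under the protocol rule = true median / (1 − *d*).

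| *d* | Inflation 1/(1 − *d*) | True median 6.0 months becomes |
|---|---|---|
| 5% | 1.05 | 6.3 |
| 10% | 1.11 | 6.7 |
| 20% | 1.25 | 7.5 |
| 30% | 1.43 | 8.6 |

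This formula censors at the date of death, whereas the protocol censors at the last scan before it. As a check, take scans every 56 days (1.84 months) and a 6-month median. The probability of an event in one interval is 1 − exp(−0.1155 × 1.84) = 0.1915. Split it into progression, 0.1915 × (1 − *d*), and death, 0.1915 × *d*. Someone who dies in an interval is no longer at risk at the scan that closes it, so the progression hazard per scan is 0.1915(1 − *d*) / (1 − 0.1915*d*). For *d* = 10%, 20% and 30% this is 0.1757, 0.1593 and 0.1422. The resulting medians (1.84 × ln 0.5 / ln(1 − hazard)) are 6.6, 7.35 and 8.3 months, an inflation of 1.10, 1.23 and 1.39. The formula is slightly high, but the direction and order of size are unchanged.

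**2. TTR, scan by scan to week 24**

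Among those still at risk, let *r* be the probability of response at each 8-weekly scan and *q* the probability of progression or death. Put *s* = 1 − *r* − *q*.

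- True cumulative response after three scans = *r*(1 + *s* + *s*²).
- Protocol rule: 1 − KM = 1 − (1 − *r*)³.

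| *r* | *q* | True | 1 − KM |
|---|---|---|---|
| 0.08 | 0.40 | 0.08 × (1 + 0.52 + 0.2704) = 14.3% | 1 − 0.92³ = 22.1% |
| 0.10 | 0.30 | 0.10 × (1 + 0.60 + 0.36) = 19.6% | 1 − 0.90³ = 27.1% |
| 0.15 | 0.30 | 0.15 × (1 + 0.55 + 0.3025) = 27.8% | 1 − 0.85³ = 38.6% |

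**3. TTR with constant hazards**

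With monthly hazards *h*ᵣ for response and *h*ₚ for progression or death:

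- true = *h*ᵣ/(*h*ᵣ + *h*ₚ) × (1 − exp(−(*h*ᵣ + *h*ₚ)*t*))
- protocol rule: 1 − KM = 1 − exp(−*h*ᵣ*t*)

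| *h*ᵣ, *h*ₚ | Month | True | 1 − KM |
|---|---|---|---|
| 0.05, 0.25 | 6 | (0.05/0.30)(1 − e^−1.8) = 14% | 1 − e^−0.3 = 26% |
| 0.05, 0.25 | 12 | (0.05/0.30)(1 − e^−3.6) = 16% | 1 − e^−0.6 = 45% |
| 0.03, 0.25 | 12 | (0.03/0.28)(1 − e^−3.36) = 10% | 1 − e^−0.36 = 30% |

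**4. TTR in one cohort of 20**

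Suppose 2 respond and 8 progress at week 8, 1 responds and 5 progress at week 16, and 1 responds and 3 have stable disease at week 24. Four of 20 respond, so ORR is 20%. The responders over those at risk are 2/20, 1/10 and 1/4, so 1 − KM = 1 − 0.9 × 0.9 × 0.75 = 39%. The report would show a 20% response rate and a response curve reaching 39% in the same 20 people.

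**The case against.** The strongest reply concerns consequence.

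- **The 12-month TTR gap sits in a thin tail.** With hazards 0.05 and 0.25, only exp(−3.6) = 2.7% are still at risk, about half a person in a cohort of 20. A constant response hazard over 12 months is also doubtful when treatment stops after three cycles. This stands. The 24-week gaps of about 8 to 11 points are the better guide.
- **The honest response percentage appears elsewhere.** ORR is a crude proportion with an exact 80% confidence interval, and Section 9.4.1 also asks for the percentage with each event. This limits the harm, but it leaves the TTR curve contradicting the ORR beside it.
- **The share of responders who die without documented progression is unknown.** Responders are scanned regularly, also after treatment ends, until progression. At a 5% share the DoR inflation is only about 5%. This stands as a limit on size.
- **No formal decision depends on either estimate.** There is no hypothesis test. Escalation and the MTD use DLTs, backfill and expansion use response counts, ctDNA and absorbed dose, and Section 4.4 singles out OS and PFS for the primary data analysis. By-participant listings would show a responder's death. This stands too.
- **Detail belongs in the SAP.** This does not answer the point. The protocol itself fixes the event, the censoring and the estimator.

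**Conclusion.** The point holds for both endpoints. As written, DoR omits death and contradicts the PFS definition in the same list. The TTR rule censors people who can no longer respond and then applies an estimator that assumes they can. No other section corrects either rule, and in expectation both errors favour the drug.

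The direction follows from the rules; the size rests on assumed rates. DoR medians are inflated by about 5% if 5% of response-ending events are deaths without documented progression, rising to about 40% if 30% are. The TTR curve is about 8 to 11 percentage points too high at 24 weeks under the per-scan rates above. Under the constant hazards it is 20 to 29 points too high at 12 months, where few remain at risk.

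The sponsor should correct this. It does not threaten the primary objectives: the endpoints are secondary and descriptive, and dose escalation and MTD determination are untouched.

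**What to change.** Amend two definitions in Protocol Section 9.4.2, and carry them into the SAP:

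1. **DoR.** Measure from the first documented response that is later confirmed to progression or death from any cause, whichever comes first. Censor at the last evaluable assessment only responders who are alive and progression-free.
2. **TTR.** Summarise descriptively (median and range) among confirmed responders. If a curve over the whole Efficacy Evaluable set is wanted, use a cumulative incidence function with progression or death as competing events. In either case delete the sentence that censors non-responders.

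No new data are needed, since deaths are already collected for OS (Sections 8.2.2 and 8.5.12). The cost is a somewhat shorter reported median DoR if responders die without documented progression, and a TTR summary that agrees with the ORR.
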